5.2. Protocol deviations

Protocol deviations are failures to adhere to the inclusion/exclusion criteria and protocol requirements and will be classified into major and minor protocol deviations. They will include, but are not limited to, protocol deviations from the site and process deviations tracked by the sponsor.

Major protocol deviations will be identified by medical review prior to database snapshot for main analysis.

The following criteria must be considered as major protocol deviations:

- 1. Violation of major inclusion or exclusion criteria
- 2. Assignment to incorrect vaccine/dose (i.e., actual vaccine/dose taken differs from the scheduled)
- 3. Non-compliance (e.g., no vaccine was administered)
- 4. Intake of prohibited concomitant medication
- 5. Missing primary endpoint data
- 6. Delayed safety reporting
- 7. Study assessments prior to signing informed consent form
- 8. Signing a non-approved version of the informed consent form.

PDs related to COVID-19 will be reported.

Major protocol deviations will be presented in a listing including information on treatment group, site, description of protocol deviation, classification, reason for deviation, coded term, date of occurrence and subject exclusion. For each group, vaccine and subgroup, the number and percentage of subjects with major protocol deviations will be summarized in total, by site and by protocol deviation type.

5.3. Subgroups

Subgroup analyses of HIV-positive subjects in Group A, of transplant subjects within Group B and of the immunology subset within Group B may be conducted as appropriate.

6. Statistical analyses

6.1. General considerations

No formal statistical testing will be done.

Unless otherwise specified, analyses will be based on data pooled across all study sites within the BNT162-14 trial.

Data assessed after a vaccination with a non-trial SARS-CoV-2 vaccine will be excluded from all statistical analyses (tables and listings) accordingly.

Notes:

- Data assessed on the same day as the non-trial vaccination will remain in the analysis.
- If the date of non-trial vaccination is missing, but month and year information is available, data assessed after the last day of the respective month will be excluded from statistical analysis.

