4.2 Scientific rationale for the trial design

The scientific rationale for this open-label trial is the following:

- to describe changes in vaccine-induced durability and T cell, B cell and antibody breadth to SARS-CoV-2 antigens before and after booster vaccines;
 - to assess if booster vaccines improve immune responses against variant B.1.351;
 - to describe changes in vaccine-induced correlates of protection (if identified from other BNT162 vaccine studies);
- to assess safety of additional BNT162 booster vaccines;
- to describe sequences of SARS-CoV-2 infections to increase understanding of the current SARS-CoV-2 strains in circulation and document if potential signs of immune pressure from vaccines, genetics, etc. on the virus are observed; and
- to assess changes in immune responses in transplant subjects with 3rd and 4th vaccinations.

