6.3 Measures to minimize bias: randomization and blinding

This is an open-label trial but:

- Group A trial subjects will be randomized 2:1 to BNT162b2s01:Comirnaty using an online randomization tool.
- Group B trial subjects will be allocated to trial treatment without active randomization and selected subjects will be asked to participate in the detailed immunogenicity assessment based on their parent trial cohort.

Page 43 of 91 Version: 4.0 Date: 20 JAN 2022

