	Group B immunology subset and will receive one injection of Comirnaty [®] which could be potentially followed 3 to 7 months afterwards by a second injection of Comirnaty [®] . This group will be referred to as Group B transplants. Subjects not eligible during this period due to any medical reason (e.g., breakthrough infection causing investigational medicinal product delay decision from the investigator) will not receive the 4 th dose in this trial. Dose : 30 µg of Comirnaty [®] or BNT162b2s01 Dosing regimen: Group A: One (at Day 1) intramuscular injection with 30 µg of either Comirnaty or BNT162b2s01. Group B: Two (at Day 1 and Day 21) intramuscular injections with 30 µg of Comirnaty, except Group B transplant subjects. Group B transplant subjects: Two intramuscular injections of 30 µg of Comirnaty, with injection 2 administered 3 to 7 months after injection 1 (Day 1). The planned time points for injection of the investigational medicinal product for Groups A and B are provided in the Schedule of Activities in the protocol (Section 1.3)
	Administration route: Intramuscular
Treatment and study duration	In total, the planned trial duration for a subject in this trial is approximately 30 weeks (≤4 weeks of screening and ~26 weeks follow-up).
Planned number of subjects	The maximum number of subjects in Group A will be 90 (including up to 15 HIV-positive subjects) and in Group B will be 459 (including up to15 transplant subjects). A subset of Group B (n=129) will be asked to participate in an immunology subset evaluation.
Randomization and blinding	Subjects in Group A will be randomized in a 2:1 ratio to either BNT162b2s01 or Comirnaty [®] . All subjects in Group B will receive at least one injection of Comirnaty [®] . They will not be randomized. The study is open-label.

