1.3. Schedule of visits and procedures

The schedule of visits and procedures can be found in the protocol in Tables 1 (Group A), 2 (immunology subset of Group B, with two injections), 2a (immunology subset of Group B transplant subjects, injection 2), and 3 (Group B without immunologic assessments).

2. Statistical hypotheses

There is no formal statistical hypothesis under test.

3. Interim analyses

No formal interim statistical analysis will be performed. However, preliminary analyses may be performed after completion of Visit 5 for any group (i.e., Group A or Group B).

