6.5.1. Neutralizing antibody titers and antibody titers (ELISA)

Definition

For each subject and each time point two titers for each variant will be determined, as each sample will be measured in replicate. The response per subject and timepoint is defined as the geometric mean of the two titers.

Analysis

Antibody titers (ELISA) derived from reference will be summarized using descriptive statistics for all time points for Group A, Group B and the immunology subset. Additionally, GMT with 95% CI will be presented.

The same analysis will be performed for antibody titers (ELISA) derived from SARS-CoV-2 variant B.1.351 for Group A only.

The antibody response will be listed.

Figures: For each vaccine type, antibody titers (ELISA) will be presented graphically displaying GMT with 95% CI at all time points (two line plots, one with linear and one with log scaled y-axis). For group A, additionally, the same plot will be created by treatment group.

The same analysis will be repeated for neutralizing antibody titers.

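### The SAP plans no effect size or interval for Group A's randomised vaccine contrast; a baseline-adjusted titer ratio with a 95% CI would supply one

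*SAP*

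**What the plan says.** Protocol 6.3 sets the allocation: "Group A trial subjects will be randomized 2:1 to BNT162b2s01:Comirnaty using an online randomization tool". The same section says of the other group that "Group B trial subjects will be allocated to trial treatment without active randomization", so Group A holds the only randomised contrast. SAP 1.2 gives its ceiling: "The maximum number of subjects in Group A will be 90".

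The plan is openly descriptive. SAP section 2 says "There is no formal statistical hypothesis under test", SAP 6.1 says "No formal statistical testing will be done", and Protocol 9.4.3 calls the trial exploratory and hypothesis-generating.

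For titers, SAP 6.1.1 tabulates Group A by vaccine and in total. The planned outputs are:

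- SAP 6.5.1: "Additionally, GMT with 95% CI will be presented", plus a plot of GMTs by treatment group.
- SAP 6.5.2: GMFR from Day 1, with 95% CI.
- SAP 6.5.3: seroconversion percentages, with 95% CI.
- SAP 6.5.4: the GMT for the reference strain divided by the GMT for B.1.351. No interval is stated for this ratio.

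SAP 5.1 assigns subjects in every analysis set to the vaccine they actually received.

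**The concern.** Every titer interval in SAP 6.5 describes one arm at a time. The ratio in SAP 6.5.4 could be mistaken for a vaccine comparison, but it sets two strains side by side. Neither SAP 6.4 to 6.6 nor Protocol 9.4 contains a between-arm ratio or difference.

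Randomisation is what would let a difference between the boosters be attributed to the vaccine. Protocol 4.3 anticipates no difference in immunogenicity between the two, and an interval for the ratio would show how far the data agree with that. As planned, a reader has two separate intervals and must either compare them by eye or reconstruct the contrast. Day 1 titer enters only through the fold rise, which uses baseline information less efficiently than regression adjustment.

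**Working it through.** The plan states no sample size calculation, SD or target difference, so there is no planned figure to reproduce. The check asks what a direct estimate would deliver.

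**Inputs from the documents.** Allocation 2:1 (Protocol 6.3). Maximum N of 90 (SAP 1.2), which agrees with the cohort counts in Protocol 4.1: 24 + 31 + 15 + 20 = 90. An exact split gives 60 and 30.

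**Assumed inputs.** Log10 titer SD of 0.4 to 0.6, equal in both arms. Correlation r between Day 1 and visit log titer: 0.5, with 0.3 and 0.7 as a range. A lower-N scenario of 30:15.

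**1. Direct interval, unadjusted.** The 95% CI is the ratio multiplied and divided by

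10^( t × SD × √(1/n₁ + 1/n₂) )

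At 60:30, √(1/60 + 1/30) = 0.2236 and t on 88 df = 1.987. For SD 0.5 the exponent is 1.987 × 0.5 × 0.2236 = 0.222, a factor of 1.67.

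**2. Direct interval, baseline-adjusted.** Multiply the exponent by √(1 − r²). For SD 0.5 and r = 0.5 it is 0.222 × 0.866 = 0.192, a factor of 1.56. (The model uses one more degree of freedom; the effect is negligible.)

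**3. Non-overlap of the two per-arm CIs.** The observed ratio must exceed the product of the two per-arm factors, each 10^( t × SD/√n ). For SD 0.5 these are 1.35 (n = 60) and 1.54 (n = 30), with a product of 2.07 before rounding.

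| Assumed log10 SD | Unadjusted factor, 60:30 | Adjusted factor, r = 0.5, 60:30 | Ratio needed for CI non-overlap, 60:30 | Unadjusted factor, 30:15 |
|---|---|---|---|---|
| 0.4 | 1.51 | 1.43 | 1.79 | 1.80 |
| 0.5 | 1.67 | 1.56 | 2.07 | 2.08 |
| 0.6 | 1.85 | 1.70 | 2.39 | 2.41 |

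At SD 0.5, an observed ratio between 1.67 and 2.07 would leave the per-arm CIs overlapping although the direct unadjusted interval excludes 1.

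**4. Gain from adjustment.** The variance gain is 1/(1 − r²): 1.10 at r = 0.3, 1.33 at r = 0.5 and 1.96 at r = 0.7. At r = 0.5 this equals about 33% more subjects.

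**5. Does the fold rise already do this?** If baseline and visit SDs are equal, the log fold rise has variance 2 × SD² × (1 − r). At r = 0.5 that equals SD², so a ratio of GMFRs has the same factor as the unadjusted ratio (1.67 at SD 0.5), against 1.56 with adjustment.

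**6. What can be recovered from the planned tables?** Each arm will have n, a GMT and a t-based CI. The log SD is √n × (log upper limit − log GMT)/t, and the arms are independent, so the unadjusted ratio and its CI follow. The adjusted ratio also needs the within-arm covariance of Day 1 and visit titers, which no output reports. It could be backed out from the Day 1 GMT, visit GMT and GMFR intervals only if exactly the same subjects fed all three. Either reconstruction would be by vaccine received.

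**The case against.** The strongest reply is that the plan is consistent with its own aim. It has no hypothesis and no powered comparison, its primary endpoints are safety endpoints, and its secondary objective is to describe change from baseline. That stands: this is an omitted estimate, not an error or a contradiction. It does not remove the point, because ruling out tests does not rule out estimation, and the SAP already reports many intervals without a test. Nor does the exclusion of exploratory analyses in SAP 6.7 cover it, since titers are secondary endpoints.

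Three stronger readings are tempting, and the documents do not support them.

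- A reader might infer that the trial cannot say how the boosters differ. It can, approximately: the unadjusted ratio follows from the per-arm output.
- A reader might take Protocol 4.2, "to assess if booster vaccines improve immune responses against variant B.1.351", as a demand for an arm comparison. It sits under a bullet about changes before and after boosting and reads most naturally as a before/after question, which the GMFR addresses.
- A reader might call comparison of two CIs by eye invalid. Non-overlap is conservative and inefficient; it does not overstate a difference.

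Baseline is also not ignored, since the GMFR is a change from baseline on the log scale. Finally, 60:30 is a best case. Protocol 10.9.3 records a shortened recruitment period because no parent-trial subjects were left to roll over, and SAP 6.1 drops data collected after a non-trial vaccination, which thins later visits.

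**Conclusion.** The point holds as a cheap improvement. The trial randomises Group A but does not plan to report an effect size or interval for that contrast. What is lost is a printed between-arm estimate, the precision from baseline adjustment, and an analysis by randomised arm.

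The precision figures are illustrative. They rest on the assumed SD and correlation, neither of which is in the documents, and on how many subjects contribute. Even at 60:30 the interval would be fairly wide, and at 30:15 it could span a factor of more than 2 either way. That is a reason to show the interval, not to claim that the trial could settle the comparison.

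**What to change.** Add to SAP 6.5.1, for Group A: a linear model of log10 titer on vaccine arm and log10 Day 1 titer, reporting the adjusted geometric mean ratio (BNT162b2s01/Comirnaty) with its 95% CI and no p-value.

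- **Lead endpoint.** Name one, for example the B.1.351 neutralizing titer at Week 4. Treat the other assays, strains and visits as supportive. Four post-baseline visits × two strains × two assays already gives 16 ratios.
- **Arm definition.** Analyse this contrast by randomised arm and say so, because SAP 5.1 currently assigns all sets as treated. The two coincide if everyone received the allocated vaccine.
- **HIV status.** Optional as a covariate. At most 15 subjects are HIV-infected, about 5 of them expected on Comirnaty, and Protocol 6.3 does not name it as a stratification factor.

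The cost is SAP wording and one standard model per assay, strain and visit; all the samples are already scheduled. The downside is a small amount of extra analysis and several supportive intervals with no ranking among them, which should be labelled descriptive.

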8.3.1 Time period and frequency for collecting AE, AESI, and SAE information

For trial subjects enrolled in this clinical trial, i.e., after transfer from the parent trial to this trial, all AEs, AESI, and SAEs (including a death) will be recorded at the time points listed in the SoA in Section 1.3. All safety reporting will occur through this rollover trial; this includes the reporting of non-vaccine related AEs that are unresolved from the parent trial.

For subjects who receive a non-trial SARS-CoV-2 vaccination, AEs/SAEs will be collected as specified above until the date when the subject was vaccinated with the non-trial SARS-CoV-2 vaccine. The AEs expected to be captured after non-trial SARS-CoV-2 vaccination are within the frame of post-marketing safety data reporting.

Investigators are not obligated to actively seek AEs or SAEs at any time after a trial subject has been discharged from the trial, however, if the investigator learns of any SAE (including a death), that they consider to be reasonably related to the IMP administration or trial participation, the investigator must promptly notify the sponsor.

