5.1. Definition of analysis sets

Screened set (SCR)

The screened set is defined as all subjects who signed informed consent.

Safety set (SAF)

The safety set is defined as all subjects who received at least one dose of investigational medicinal product (IMP).

Safety boost set (SAFB)

The safety boost set is defined as all subjects who received two doses of IMP (first injection (Dose 1) and second injection (Dose 2)).

Note: Group A will be excluded from the SAFB as they receive only a single injection according to protocol.

Immunogenicity set (IMM)

The immunogenicity set is defined as all subjects who received at least one dose of IMP and have at least one post-baseline functional antibody titer (e.g., VNT or an equivalent assay) immunogenicity assessment.

Note: The expression 'have at least one post-baseline functional antibody titer immunogenicity assessment' refers to having either at least one post-baseline neutralizing antibody titer or one post-baseline ELISA titer immunogenicity assessment.

Immunogenicity per-protocol set (IMMPP)

The immunogenicity per-protocol set is defined as all subjects included in the immunogenicity set that have no major protocol deviations as determined by the clinician and who received two doses of IMP (first injection (Dose 1) (for Group A and B) and second injection (Dose 2) (only for Group B)).

Note: Subjects with any major protocol deviation thought to interfere with either the mechanism of action or immunogenicity test measurements will be excluded from IMMPP set.

Note: The definitions of all analysis sets apply within the BNT162-14 trial. In all analysis sets, subjects will be assigned to the treatment groups (i.e., vaccine type) according to the actual treatment they received ("as treated"). The condition of receiving two doses of IMP will not apply to Group A.

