6.1.1. Tables and listings

Tables

In general, data will be summarized as follows:

- Group A by vaccine [Comirnaty[®], BNT162b2s01], and total
- Group A subjects having received Comirnaty[®] by HIV infection status
- Group A subjects having received BNT162b2s01 by HIV infection status
- Group B by transplant status, and total
- Group B immunology subset by transplant status, and total

Descriptive summary tables and figures will be based on scheduled visits.

Continuous variables will be summarized using the following descriptive statistics: number of subjects with non-missing data (n), mean, standard deviation (SD), median, minimum (min) and maximum (max).

Descriptive statistics of titer and fold rise of titer will additionally include geometric mean and its two-sided 95% confidence interval (CI). The geometric mean titer (GMT) is calculated as the mean of the logarithm of the functional antibody titers, backtransformed into the original scale. Two-sided CIs will be obtained by calculating CIs using t-distribution for the mean of the logarithmically transformed assay results and transforming the limits back to the original scale.

Geometric mean fold rise (GMFR) is calculated as the mean of the difference of logarithmically transformed assay results (post vaccination time point – pre vaccination time point) and back-transformed into the original scale. Two-sided CIs will be obtained by calculating CIs using Student's t-distribution for the mean difference of the

logarithmically transformed assay results and transforming the limits back to the original scale.

Categorical variables will be summarized presenting absolute and relative frequencies (n and %) of subjects in each category (including the category 'missing' if applicable). Percentages will be calculated based on the number of subjects in the respective analysis set (N) as denominator if not stated differently. Percentages may be presented with exact 95% Clopper-Pearson CIs.

SDs and CIs will only be calculated if values from at least 3 subjects are available.

Listings

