6.4. Primary endpoint analyses

The primary endpoints are solicited local reactions at the injection site occurring up to 7 days after each injection, solicited systemic reactions occurring up to 7 days after each injection, the proportion of subjects with at least one serious adverse event (SAE) occurring up to 26 weeks after the first injection, the proportion of subjects with at least one adverse event of special interest (AESI) occurring up to 26 weeks after the first injection and the proportion of subjects with at least one unsolicited treatment emergent adverse event (TEAE) occurring up to 28 days after each injection.

All primary analyses will be performed using the SAF and analyses of adverse events for Group B will possibly be repeated using the SAFB.

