6.4.1. Solicited local reactions

Definition

Solicited local reactions at the injection site consist of pain, tenderness, erythema/redness, and induration/swelling. These are assessed by the subject in a diary as stated in the protocol Section 8.2.4.

Local reactions will be graded based on the criteria given in the United States (US)Food and Drug Administration (FDA) Guidance for Industry 'Toxicity Grading Scale for Healthy Adult and Adolescent Volunteers Enrolled in Preventive Vaccine Clinical Trials' for 'Local Reaction to Injectable Products'. The grading of local reactions to injectable product is detailed in Section 10.3.2.1 (Table 5) of the protocol. The grades are Grade 1 (mild), Grade 2 (moderate), Grade 3 (severe), and Grade 4 (potentially life threatening).

The solicited local reactions will be evaluated for each injection, i.e.

- First injection (Dose 1) up to day 7 (inclusive) after first injection (Group A, immunology subset of Group B)
- Second injection (Dose 2) up to day 7 (inclusive) after second injection (Dose 2) (immunology subset of Group B)
- Both intervals combined (immunology subset of Group B)

The intervals will start with the date and time of the injection.

Note: The interval 'first injection (Dose 1) up to day 7 after first injection (Dose 1)' includes study day 1 to study day 7. This applies to the other intervals accordingly.

All analyses are based on local reactions independent of their relatedness to IMP.

Analysis

All analyses will only be performed for Group A and immunology subset of Group B.

Local reactions with missing time and occurring on the day of first injection (Dose 1) will be assigned to all intervals starting with the first injection (Dose 1). Local reactions with missing time and occurring on the day of the second injection (Dose 2) will be assigned

to all intervals including the second injection. Local reactions with missing date will be assigned to each of the applicable intervals if it cannot be ruled out, that it belongs to the time interval.

The number and percentage of subjects reporting at least one local reaction in each applicable time interval will be summarized for any local reaction and by worst grade.

The denominator of the percentages will be the number of subjects with any information on local reactions in the diary available in the respective time interval.

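### Subjects whose event collection stops at a non-trial SARS-CoV-2 vaccination stay in the 26-week SAE and AESI denominators, so the crude proportions are biased low to the extent that such vaccinations occur before Week 26

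*SAP*

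**What the plan says.** **Target.** SAP 6.4 lists among the primary endpoints "the proportion of subjects with at least one serious adverse event (SAE) occurring up to 26 weeks after the first injection", and the same for AESIs. Nothing limits this to the time before another vaccine.

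**Numerator.** Protocol 8.3.1 says that, for subjects with a non-trial vaccination, "AEs/SAEs will be collected as specified above until the date when the subject was vaccinated with the non-trial SARS-CoV-2 vaccine". SAP 6.2 repeats the rule, and SAP 6.1 adds: "Data assessed after a vaccination with a non-trial SARS-CoV-2 vaccine will be excluded from all statistical analyses". Data from the day of the vaccination itself are kept.

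**Denominator.** SAP 6.4: "All primary analyses will be performed using the SAF". SAP 5.1 puts everyone with at least one dose into that set and requires no length of follow-up. SAP 6.1.1: "Percentages will be calculated based on the number of subjects in the respective analysis set (N) as denominator if not stated differently".

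**Exceptions.** SAP 6.4.1 departs from the default for diary data: "The denominator of the percentages will be the number of subjects with any information on local reactions in the diary available" in the interval. SAP 6.5.3 does likewise for seroconversion. SAP 6.4.3 sets no other denominator for SAEs or AESIs.

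**Incomplete follow-up.** SAP 6.1.3 imputes only values beyond laboratory or assay limits. SAP 6.1.1 reports dropouts with whatever data they have. Neither document gives a censoring, person-time or at-risk rule for SAEs and AESIs. SAP 6.5 treats outside vaccination as a concurrent event for immunogenicity only.

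**The concern.** The endpoint is a risk over a fixed 26 weeks, but a subject vaccinated outside the trial at, say, Week 14 can contribute an event for only 14 of them. The planned calculation treats the remaining 12 weeks as observed and event-free. Cutting follow-up can remove subjects from the numerator but never from the denominator, so the error can only be downward or zero.

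At stake is the primary safety result: a proportion labelled as a 26-week risk that rests on less than 26 weeks for some subjects, and an interval computed as if all had been followed throughout.

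The disposition table may not reveal this. Protocol 4.4 defines completion by planned visits. The schedule footnotes let non-transplant subjects continue after an outside vaccination without sampling and with information taken remotely. Such a subject could be counted as a completer although event collection has ended.

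**Working it through.** The plan states no expected SAE or AESI rate, no power and no uptake rate, so there is no figure to reproduce. The direction follows from the rules above; the size needs assumptions.

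**Inputs**
- From the documents: horizon 26 weeks; maximum N of 90 (Group A) and 459 (Group B).
- Assumed: true 26-week risk p = 5%; share f vaccinated outside the trial before Week 26; week of that vaccination T; a hazard that the outside vaccination does not change.

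**Formula (constant hazard)**

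Expected crude proportion = (1 − f)·p + f·E[1 − (1 − p)^(T/26)]

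For p = 5% the expectation term is:
- T uniform over Weeks 0-26: 1 − 0.05/0.05129 = 0.0252
- T uniform over Weeks 12-26: 1 − [(0.9766 − 0.9500)/0.05129]/(14/26) = 0.0368

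Example, f = 60%, Weeks 12-26: 0.4 × 0.05 + 0.6 × 0.0368 = 0.0421, and 0.0421/0.05 = 0.84.

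| Uptake f | Weeks 12-26: ratio (5.0% prints as) | Weeks 0-26: ratio (5.0% prints as) |
|---|---|---|
| 5% | 0.99 (4.9%) | 0.975 (4.9%) |
| 10% | 0.97 (4.9%) | 0.95 (4.8%) |
| 20% | 0.95 (4.7%) | 0.90 (4.5%) |
| 30% | 0.92 (4.6%) | 0.85 (4.3%) |
| 60% | 0.84 (4.2%) | 0.70 (3.5%) |

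The ratios hardly depend on p between 1% and 10%.

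**Front-loaded risk.** Suppose 60% of the 26-week risk falls in the first 4 weeks and outside vaccination is uniform over Weeks 4-26. The ratio is then approximately 1 − f × 0.4 × 0.5, which gives 0.98, 0.94 and 0.90 for f = 10%, 30% and 50%.

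**Precision.** With no events, the Clopper-Pearson upper limit is 1 − 0.025^(1/N). Scale N by the share of follow-up observed, taking f = 30% and Weeks 0-26:
- Group A: 4.0% at N = 90, against 4.7% at 90 × 0.85 = 76.5
- Group B: 0.80% at N = 459, against 0.94% at 459 × 0.85 = 390

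**Events missed.** At a true 5% with Weeks 12-26 timing:
- Group A, f = 60%: 90 × (0.0500 − 0.0421) = 0.7 of 4.5 expected subjects with an event
- Group B, f = 20%: 459 × (0.0500 − 0.0474) = 1.2 of 23
- Group B, f = 60%: 459 × (0.0500 − 0.0421) = 3.6 of 23

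**Does censoring repair it?** In a simulation (4,000 runs per setting, N = 90 and 459, p = 5%, Weeks 0-26), crude n/N averaged about 4.8%, 4.2-4.3% and 3.7-3.8% for f = 10%, 30% and 50%. Kaplan-Meier censored at the outside vaccination averaged 5.0-5.1% throughout. The simulated censoring was non-informative by construction.

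**The case against.** The best defence is that n/N answers a legitimate question: the risk of an event before any other vaccine. Protocol 8.3.1 deliberately assigns later events to post-marketing reporting. Excluding them is defensible, and for that target n/N is not biased. This stands as a possible target, but neither document states it, and the endpoint reads as an unqualified 26-week risk.

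Three stronger readings are tempting, and the documents do not support them.

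- *The primary risk is materially understated.* No uptake rate is given. Every subject receives a trial vaccine on Day 1. The footnotes that stop sampling are attached to late visits: 6 and 7 in Protocol Tables 1 and 2, 11 and 12 in Table 2a, and 7 in Table 3. That suggests late timing, although Protocol 6.5 records outside vaccines from after Visit 0. The 0.70 ratio is an extreme of the assumed range.
- *Amendment 03 shows that high uptake was expected.* Its overall rationale (Protocol 10.9.3) is Dose 2 for transplant subjects and a shorter recruitment period. The edits on outside vaccination provide for the event; they do not forecast its frequency.
- *Safety comparisons between groups are invalidated.* The trial is descriptive, with no hypothesis or testing and no planned between-group safety comparison. Groups A and B already differ in priming and doses. Differing uptake is possible but undocumented.

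It is also fair that fewer than one expected event is missed in Group A in the late-timing cases, and that outside vaccinations are recorded and listed (Protocol 6.5, SAP 6.3.2). A listing does not correct the proportion. The Safety Set denominator comes from the SAP's default rule and not from a sentence specific to SAEs or AESIs, but nothing overrides it.

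**Conclusion.** The point holds in conditional form. As written, SAP 6.1, 6.1.1 and 6.4 together count a subject with no event before a non-trial vaccination as event-free through Week 26. To the extent that such vaccinations occur before Week 26, the crude SAE and AESI proportions underestimate the stated endpoint, and any interval based on the full N is too narrow.

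The size cannot be fixed from the documents. It is negligible at 5-10% uptake with late timing, becomes relevant if uptake is high or early, and shrinks if risk is concentrated soon after injection. The calculated ranges rest on assumed uptake and timing, a constant hazard except in the front-loaded case, and outside vaccination that neither changes the event rate nor depends on the subject's risk.

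The matter is worth correcting because the remedy is cheap, not because a large bias has been shown.

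**What to change.** In SAP 6.4.3:

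1. Keep n/N for SAEs and AESIs, labelled as events before any non-trial SARS-CoV-2 vaccination.
2. Add, separately for SAE and AESI, a 26-week cumulative incidence by Kaplan-Meier with 95% CI, censored at non-trial vaccination or withdrawal, or else an exposure-adjusted rate. Apply the date rules already in SAP 6.1. State the non-informative censoring assumption: if subjects who are ill put off an outside vaccine, those still under observation carry higher risk and the estimate leans high.
3. Report per group the number and timing of non-trial vaccinations and the number with complete 26-week event follow-up.

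The time origin must be settled first: SAP 6.4.3 runs the SAE and AESI window from signature of the consent form, whereas SAP 6.4 runs it from the first injection. The two must be reconciled.

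The cost is SAP wording and one extra table. Non-trial vaccinations are already recorded in the CRF, and SAP 6.1 already relies on their dates. Intervals will be wider, and the reported risk may be slightly less favourable.
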